11.2 Secondary Efficacy Analyses

Secondary Analyses of Primary Outcome: The primary analysis as described in section 11.1 will be repeated in analysis populations 2-8 as given in section 9.3 overall and by subgroups described in section 9.4. For analysis population 1, the primary analysis as described in section 11.1 will be repeated in subgroups described in section 9.4.

In addition, multivariable GEE regression analyses will be conducted separately in populations 1-8 from section 9.3, where the primary composite outcome is modelled using individual and practice level predictors in addition to the CAPTURE intervention group. Interactions will be assessed.

Efficacy Analyses of Secondary Outcomes: All analyses in this section will be conducted (separately) for each study population 1 through 8 described in section 9.3 overall and by subgroups described in section 9.4.

We will use the GEE framework to study and describe each of the individual components of the composite outcome as they relate to the CAPTURE intervention group.

In the subset of patients who report being current smokers at baseline, we will study additional binary outcomes, such as incidence of physician counselling/recommendation to stop smoking, physician referral to a formal smoking cessation program, newly prescribed smoking cessation medication, and referral to a smoking quit line, individually and in a composite outcome that also incorporates the primary outcome components.

Multivariable GEE models will incorporate individual and practice level covariates into the analysis of individual components of the composite outcome. Model selection in multivariable secondary analyses will be based on statistical significance at the 0.05 level using GEE robust sandwich estimation of variability within clusters. Model fit will be checked by comparing observed versus predicted values within predefined subgroups of interest as given in section 9.4.

Change in CAT score and change in number of episodes of respiratory illness requiring antibiotic/steroid treatment will be analyzed using mixed⁵ models with a random effect for practice. The average cluster sample proportion of patients who experience exacerbations will be compared between intervention groups using methodology similar to that used for the primary endpoint. Subject to having sufficient mortality events, survival analysis⁶ allowing for correlation of endpoints within cluster (practice) will be used to compare mortality between intervention groups and perform multivariable analysis. We will explore differences between intervention groups in the average cluster sample rate of hospitalizations again using GEE.

Secondary Analyses Using Single Imputation: Primary and secondary efficacy analyses of outcomes collected via both medical record review and patient survey will be repeated among patients with complete medical record review data, imputing a single value for missing outcome components from the patient survey. One analysis will impute a negative outcome (i.e., the event did not occur) for each missing survey response; another analysis will impute a positive outcome (i.e., the event did occur) for each missing survey response. Complete-data analyses described in sections 11.1 and 11.2 will be performed on each complete data set produced by imputation.

Secondary Analyses Using Multiple Imputation: Primary and secondary efficacy analyses will be repeated using data sets generated by the multiple imputation procedure described in section 9.5. Complete-data analyses described in sections 11.1 and 11.2 will be performed on each complete data set produced by multiple imputation. Parameter estimates and standard errors will be

combined across the multiply imputed data sets using the method of Rubin⁸, which is implemented by the `pool()` function in the R package ‘mice’. Specifically, for each parameter of interest, let Q_i be the parameter estimate from data set i , with associated complete-data variance U_i . Let m be the number of imputed data sets. Then

$$\bar{Q} = \frac{1}{m} \sum_{i=1}^m Q_i \text{ (the average of the } m \text{ estimates)}$$

is the overall parameter estimate. Let

$$\bar{U} = \frac{1}{m} \sum_{i=1}^m U_i \text{ (the average of the } m \text{ variances)}$$

and

$$B = \frac{1}{m-1} \sum_{i=1}^m (Q_i - \bar{Q})^2 \text{ (the variance in estimates between data sets).}$$

Then the overall parameter estimate \bar{Q} has variance estimated by

$$T = \bar{U} + \left(1 + \frac{1}{m}\right) B$$

A confidence interval and p-value for the test of whether the parameter is non-null will be computed from \bar{Q} and T based on a t distribution.

12 Safety Analyses

Safety data, including AEs and SAEs will be summarized descriptively overall and by treatment group for the safety population. Coding into organ system will be performed by the study chairs for AEs and SAEs. The following organ systems will be summarized: cardiovascular disorders, dermatological disorders, gastrointestinal disorders, hematological disorders, metabolic disorders, musculoskeletal and connective tissue disorders, neurological disorders, psychological disorders, pulmonary disorders, renal and urinary disorders, hepatobiliary disorders, and other disorders.

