| Assess the impact of CAPTURE education and patient-level CAPTURE information on clinician interventions specific to smokers who are CAPTURE+. | Proportion of CAPTURE+ participants currently smoking at the baseline study visit who have any of the components of the Aim 3 primary endpoint or any of the following occur within 12 months of baseline (evaluated as a composite endpoint and as individual endpoints): 1) clinician counseling or recommendation for smoking cessation, 2) referral to a smoking cessation program, 3) referral to a smoking quit line, and 4) newly prescribed medication for smoking cessation. |
| Determine the impact of CAPTURE education and patient-level CAPTURE information on patient symptoms, exacerbations, hospitalizations, and mortality among CAPTURE+ patients. | In CAPTURE+ participants, change in CAT score between baseline and follow-up at 12 months after baseline, and proportion of patients who experience exacerbations, hospitalizations, or mortality within 12 months of baseline. |
| Determine the impact of CAPTURE education and patient-level CAPTURE information on identification and management of patients with respiratory burden. | All of the above endpoints for Aim 3, in the population of participants defined by each of the following instead of CAPTURE+ status: 1) clinically significant COPD, 2) spirometric COPD, 3) preserved ratio, impaired spirometry (PRISM), and 4) symptomatic non-obstructed (SNO). |
| Determine the potential impact of SARS CoV-2 infection on clinical actions taken in response to CAPTURE screening. | All of the above endpoints for Aim 3, in all of the analysis populations named above, separated into cohorts based on enrollment date and the degree to which follow-up may have been affected by the SARS-CoV-2 pandemic. |

6 Study Methods for Cluster Randomized Trial (CAPTURE Protocol Aim 3)

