| Preserved ratio, impaired spirometry (PRISm) | Participants without spirometrically defined COPD who have post-bronchodilator $FEV_1 < 80\%$ predicted. Among participants who do not complete post-bronchodilator spirometry and have pre-bronchodilator $FEV_1/FVC \geq 0.7$, those with $FEV_1 \geq 80\%$ predicted will be considered not to have PRISm and those with $FEV_1 < 80\%$ predicted will be considered to have undetermined PRISm status in primary analyses. |
| Symptomatic non-obstructed (SNO) | Participants without spirometrically defined COPD and without PRISm who have a COPD Assessment Test score ≥ 10 . |

Longitudinal Follow-up

A pre-defined subgroup of enrolled participants, who meet any of the below criteria, will undergo longitudinal follow-up at 12 months:

1. CAPTURE+ participants, as defined above.
2. Participants who have spirometrically defined COPD, as defined above, or post-bronchodilator $FEV_1 < 80\%$ predicted at baseline. If post-bronchodilator spirometry is not completed, then pre-bronchodilator $FEV_1 < 70\%$ predicted will be considered to satisfy this criterion for follow-up.
3. A random sample of approximately 5% who do not meet criteria 1 – 2.

Participants who meet the criteria for follow-up will be sent notification/reminder letters within the first three weeks of enrollment and at three, six, and nine months. Patient-reported data will be collected by COPD Foundation via telephone, secure web-based server, or mail-based methodologies, based on participant preference.

Subject medical data will be collected from the medical record to assess for changes in practice-level care.

[figure not shown]

Figure 1

The hypothesis for Aim 3 is that sites where COPD and CAPTURE education and patient-level CAPTURE data are provided to clinicians will exhibit improved COPD diagnosis and COPD-related care compared to sites where COPD education is provided to clinicians.

7 Inclusion-Exclusion Criteria and General Study Population for Aim 3

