9.4 Covariates and Subgroups

The effect of the CAPTURE intervention will be explored in predefined subgroups of interest with results tabulated (estimated difference in average proportion of CAPTURE+ patients per practice meeting composite endpoint between intervention arms by subgroup, corresponding 95% confidence interval and p-value) as well as displayed via forest plots. These analyses will proceed similarly to that described for the primary endpoint in section 11.1. Individual-level covariates used to define subgroups of interest are categorical age (45-59 years, 60-69 years, 70-80 years), gender (Male, Female), race (American Indian/Alaska Native, Asian, Native Hawaiian or Other Pacific Islander, Black or African American, White, Unknown or Not Reported), ethnicity (Hispanic/Latino, Non-Hispanic/Latino, Unknown or Not Reported), educational status (Less than High School Graduate, High School Graduate/GED, Vocational/Some College, College Degree, Professional/Graduate Degree, or Not Reported), insurance status (private, public, none), living arrangements (alone, not alone), employment status (working, not working, unknown), smoking status (Current, Former, Never), asthma history, baseline respiratory medications (short-acting bronchodilator, maintenance respiratory medication, or none), cardiac morbidity, COPD Assessment Test (CAT) score (10 or above versus less than 10), BMI (Below 25.0 [Normal/Underweight], 25.0-29.9 [Overweight], 30.0-39.9 [Obese], 40.0 and Above [Severely Obese]), as well as cohorts defined in section 6.1 (Spirometrically Defined COPD, Clinically Significant COPD, Mild COPD, No COPD by Spirometry, PRISm, and SNO). Practice level covariates include practice type (Part of large health system/ACO/similar, Part of academic medical center/health system, Federally Qualified Health Care Center, Independent practice, Other), location (Rural, Non-rural), being a residency site, having in-house spirometry, and number of MD/DO/NP/PA primary care clinicians (0-4, 5-9, 10 or More). Because of the possible impact of the SARS-CoV-2 pandemic on study outcomes, these analyses will be repeated in subgroups defined by whether the one-year follow-up period had entirely elapsed by March 19, 2020 (date when PBRNs paused study enrollment due to SARS-CoV-2); that is, the analyses will be repeated separately in the cohort with baseline visit completed on or before March 19, 2019, and separately in the cohort with baseline visit completed after March 19, 2019. Chart review and patient follow-up survey need not be completed by March 19, 2020 for a patient to be categorized as having pre-pandemic follow-up for this subgroup analysis.

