Multiple imputation of missing values in the baseline and 12-month follow-up data will be used to create 20 complete data sets. The set of patients included in each data set will be all of those selected for 12-month follow-up. The imputation method will be multivariate imputation by chained equations (MICE)⁶ as implemented in the R package 'mice'⁷.

Missing values of baseline spirometry FVC % predicted and FEV₁ % predicted will be imputed using linear regression models with the following predictors: age, gender, height, race, education, BMI, CAT score, asthma history, short-acting bronchodilator use, maintenance respiratory medication, and any follow-up outcomes for which baseline spirometry measurements will serve as predictors (selection of those predictors is described below). Predicted FVC and FEV₁ volumes will be calculated from the NHANES reference equations, allowing for calculation of the FVC, FEV₁, and FEV₁/FVC corresponding to the imputed % predicted values as needed.

For the purpose of organizing the imputation procedures, the 12-month follow-up outcomes will be grouped as follows:

- Pulmonary care outcomes:
 - Spirometry referral/completion
 - New diagnosis of COPD
 - New prescription for respiratory medication
 - Referral to pulmonologist or other respiratory specialist
 - Pulmonary rehab referral/completion
- Flu vaccination:
 - Flu shot recommended/ordered/administered
- Smoker-specific outcomes:
 - Counseling/recommendation for smoking cessation
 - Smoking cessation program referral/completion
 - New prescription for smoking cessation medication
 - Referral to a smoking quit line

Missing values of follow-up outcome variables, all of which will be binary (yes or no), will be imputed

using logistic regression models. For each outcome variable, the predictors will include, minimally, the following:

- All other variables from the medical record review and follow-up survey within the same group of outcomes. That is, medical record review data will be used to impute missing follow-up survey data, and follow-up survey data will be used to impute missing medical record data.
- Intervention group interacting with CAPTURE status. Intervention group must be included to avoid bias when using the imputed data to estimate the intervention effect. Interaction with CAPTURE status is included because the intervention effect is hypothesized to depend on the different recommendations associated with being classified as CAPTURE+ vs CAPTURE-.

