Then using the **geeglm** function from the **geepack** package, the R code to run the primary analysis is

```
geeglm(MetComp ~ CAPTURE,
       family = binomial(link = "identity"),
       data = final,
       id = Practice,
       corstr = "exchangeable")
```

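### The pooled No-COPD and SNO effects describe the patients selected for follow-up, not the populations named

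*SAP*

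**What the plan says.** SAP 6.1 selects three groups for 12-month follow-up: all CAPTURE+ participants; all with spirometric COPD or an FEV1 below the stated cut-off; and "A random sample of approximately 5% who do not meet criteria" 1 and 2.

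SNO is defined in SAP 6.1 without reference to CAPTURE status: "Participants without spirometrically defined COPD and without PRISm who have a COPD Assessment Test score" of at least 10. No COPD, listed as population 6 in SAP 9.3, is not split by CAPTURE status either. SAP Table 1 sets the secondary endpoints "in the population of participants defined by each of the following instead of CAPTURE+ status" and names SNO among those populations. It does not name No COPD.

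SAP 11.2 states: "The primary analysis as described in section 11.1 will be repeated in analysis populations 2-8 as given in section 9.3 overall and by subgroups". The model in SAP 11.1 is an identity-link exchangeable GEE with the arm indicator as its only covariate. The code given there has no weights argument.

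On imputation, SAP 9.5 confines each multiply imputed data set to patients selected for follow-up. It also explains one term of the imputation model: "Interaction with CAPTURE status is included because the intervention effect is hypothesized to depend on the different recommendations" attached to a CAPTURE+ or CAPTURE− result.

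The log for Amendment 2.0 in Protocol section 14 records that follow-up based on a CAT or CAPTURE score alone was dropped. Patients already selected that way stay in follow-up and are noted as such.

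**The concern.** SNO and No COPD each combine patients selected with certainty and patients selected at about 1 in 20. Without weights, the first kind dominates. If the effect differs by CAPTURE status, as the SAP itself hypothesizes, the pooled coefficient depends on the follow-up rule as well as on the population. A table row headed SNO or No COPD would then be read as the effect in all such primary care patients, while it mainly reflects those who screened positive.

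Among the populations named in SAP Table 1, only SNO is exposed. Clinically significant COPD, spirometric COPD and PRISm fall under the second selection criterion and are followed in full.

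**Working it through.** The SAP gives no figure for the make-up of the followed No-COPD or SNO sets. The one stated figure for the model being reused is the power in SAP section 8 (5% versus 15%, ICC 0.05, 44 clusters per arm, 5 CAPTURE+ each). It reproduces: effective n per arm = 44×5/(1+4×0.05) = 183, which gives power 0.894 against the stated 0.89. It has no bearing on composition.

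**Inputs (SAP 13.1, March 2020)**
- Patients, Table 6: 663+750+431+280+468+446 = 3,038.
- Practices, Table 6: 15+15+9+6+11+12 = 68.
- Patients per practice: 3,038/68 = 44.68.
- CAPTURE+ per practice: 10. Spirometric COPD per practice: about 2.
- No COPD per practice: 44.68 − 2 = 42.68. Of these, 8 are CAPTURE+ if both COPD patients are CAPTURE+, and 10 if neither is.

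**CAPTURE+ share of No COPD:** f = 8/42.68 = 0.1874 to 10/42.68 = 0.2343, so about 19-23%.

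**CAPTURE+ share of followed No COPD.** Let a be the share of CAPTURE− No-COPD patients with PRISm. Let r be the share of the remaining CAPTURE− patients retained under the earlier criteria. The documents give neither, so both are assumed.

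Selection probability among CAPTURE−: s = a + (1−a)[r + 0.05(1−r)]. Followed share = f / [f + (1−f)s].

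| a | r | s | Followed share |
|---|---|---|---|
| 0 | 0 | 0.05 | 0.82-0.86 |
| 0.15 | 0 | 0.1925 | 0.55-0.61 |
| 0 | 0.20 | 0.24 | 0.49-0.56 |
| 0.15 | 0.20 | 0.354 | 0.39-0.46 |

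First row, lower end: 0.1874/(0.1874 + 0.8126×0.05) = 0.822. Last row, upper end: 0.2343/(0.2343 + 0.7657×0.354) = 0.464. The rows with r = 0 are upper bounds for their value of a.

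**What this does to an effect (illustration only).** Take 50 patients per practice, with No COPD made up of 9 CAPTURE+, 4 CAPTURE− PRISm and 35 other CAPTURE−. Assume no retention, and effects of +10 points in CAPTURE+ and 0 in CAPTURE−. The effect in the named population is 10×9/48 = 1.9 points. In the followed mix it is about 10×9/(9+4+35×0.05) = 6.1. Simulating 100 practices at ICC 0.05 gave a mean of 6.0 for the unweighted GEE (empirical SE 1.6). Weighting by inverse selection probability gave 1.9 (SE 2.6). With equal stratum effects the two targets coincide.

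**SNO.** SNO excludes PRISm, so under the current rule every CAPTURE− SNO patient is selected at about 5%. The CAPTURE+ share of SNO is not given. Nor is the number retained under the dropped CAT criterion, whose cut-off of 10 is also the SNO cut-off. I therefore give no size for SNO.

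**The case against.** The strongest reply is that the plan largely handles this already. SAP 11.2 repeats the analysis in populations 1 and 2 by the SAP 9.4 subgroups, and those include "Mild COPD, No COPD by Spirometry, PRISm, and SNO". The CAPTURE+ and CAPTURE− strata of both populations are therefore pre-specified. SAP 9.5 and Protocol 9.2 say that the analysed patients are those with follow-up data, and the CONSORT diagram will show how many were selected. The same selection rule applies in both arms, so the comparison is fair within the followed set. Protocol 9.1.2.2 calls these analyses exploratory.

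All of that stands. It limits the harm and makes the remedy nearly free. It does not settle which rows are the reported result, and the overall row would still carry the name of a population it does not represent.

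Three stronger readings are tempting, and the documents do not support them:

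- A reader might infer that the followed SNO set must be overwhelmingly CAPTURE+. Patients retained under the earlier criteria would reduce that imbalance, and their number is unknown.
- A reader might infer that a pre- versus post-pandemic comparison in SNO is distorted by the change in selection rule. SAP 9.4 repeats the analyses "separately in the cohort with baseline visit completed on or before March 19, 2019" and separately in the later cohort, and plans no comparison between the two.
- A reader might try to bound the number retained from the monthly enrolment rates in SAP 13.1. Counting back 12 months at 100-125 per month leaves about 1,540-1,840 patients enrolled by then. The 380 eligible for survey in Table 9 are only 21-25% of these. About 28% would be expected even with no retention and no CAPTURE− PRISm. If eligible means everyone selected who had reached 12 months, the assumed rates do not fit that period, so such a bound is not reliable.

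**Conclusion.** The point holds as one about which population the estimate describes, and it is minor. As planned, the pooled No-COPD and SNO estimates apply to patients selected for follow-up. For No COPD, CAPTURE+ patients move from about 19-23% of the population to at most 82-86% of those followed, and to 39-46% under the more moderate assumptions shown. These figures rest on the March 2020 averages and on assumed PRISm and retention shares. For SNO the direction under the current rule is the same, but the size is undetermined. Any distortion of the effect requires the intervention to work differently in CAPTURE+ and CAPTURE− patients. The SAP hypothesizes this but does not quantify it.

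A reader might infer that the randomized comparison or the primary result is biased. Neither follows: the arm contrast is valid for the followed mix, and the primary analysis is confined to CAPTURE+ patients, all of whom are selected.

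**What to change.** In SAP 9.3 and 11.2:

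1. Make the CAPTURE+ and CAPTURE− strata, already available through SAP 9.4, the reported SNO and No-COPD results.
2. Label any unweighted pooled row as applying to participants selected for follow-up. Give population 2 and the CAPTURE− No-COPD stratum the same label, because they still mix patients followed in full with the 5% sample.
3. Add, as a sensitivity analysis only, a pooled estimate weighted by the inverse of the selection probability. Patients selected under the earlier CAT or CAPTURE-score criteria, who are flagged according to the Amendment 2.0 log, need their own selection probability. Report their number by CAPTURE status.

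The cost is SAP wording, table labels and one weighted run, with no new data. The downside is precision. With 5,000 enrolled, no retention and a = 0 to 0.15, the 5% sample holds about 0.05×5,000×(42.68/44.68)×(1−f)×(1−a) = 155-195 patients, and only some of them are SNO. The CAPTURE− strata and the weighted estimate will therefore be imprecise, which is why the weighted estimate should not be the main one.

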8.1 Primary Objectives

Aim 3: Define the impact of CAPTURE information provided to clinicians in identifying and managing patients with respiratory symptoms (CAPTURE+) across a broad range of primary care settings.

8.2 Practice Behavior in Sites With Vs Without Capture Education and Patient Level Capture Data Provided

Primary Hypothesis 3: Sites where basic COPD and CAPTURE education are provided to clinicians, along with patient level CAPTURE data, will have a higher probability than control sites (i.e., those receiving only basic COPD education) of meeting the composite endpoint in their CAPTURE+ patients within 12 months of baseline.

From medical record review and follow-up patient survey responses, the composite endpoint is met if one of the following is recorded: 1) referral for or completion of clinical spirometry testing, 2) new clinical diagnosis of COPD, 3) newly prescribed respiratory medication (long acting bronchodilator or anti-inflammatory for respiratory condition), 4) referral to a specialist for respiratory evaluation/ treatment, or 5) referral for or completion of pulmonary rehabilitation.

The study will enroll 50 CAPTURE practices and 50 control practices; each practice will enroll 50 patients (for a total of 5,000 patients). We project that within each practice there will be at least five patients previously undiagnosed with COPD who have a CAPTURE+ screening result. The primary analysis will be to compare the average proportion of CAPTURE+ patients per practice that meet the composite endpoint in the two intervention arms. For power and sample size computations, this is a cluster randomized trial of n=50 clusters (practices) per intervention arm with 5 CAPTURE+ patients per cluster (practice). The primary power calculation is based on comparing the average cluster sample proportion (average proportion of CAPTURE+ patients per practice meeting composite endpoint) between intervention arms. Table 5 displays power for a two-sample test comparing average cluster sample proportions, accounting for possible intra-cluster correlation coefficient (ICC) values of 0.05, 0.10 and 0.15 that are typically seen in cluster randomized trials of behavioral interventions

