(<https://www.abdn.ac.uk/hsru/research/research-tools/study-design/>). These calculations assume a type I error of 5% and that the control arm meets the composite endpoint in 5% of CAPTURE+ patients, and the CAPTURE arm meets the composite endpoint in higher percentages (columns of Table 5). There will be variability in the actual number of CAPTURE+ patients per practice. It is standard practice to inflate the number of needed clusters by 12% to account for this extra source of variability. Therefore, our power calculations are based on 44 clusters per intervention arm.

9 General Analysis Considerations

| | | | | | |
|---|-------|------|------|-------|-------|
| Overall power to detect a difference in rate of meeting primary endpoint in CAPTURE group (50 practices/cluster) vs usual care (50 practices/cluster), assuming 5% performance rate in usual care; 50 patients total / practice; assuming 10% prevalence gives 5 CAPTURE+/practice. | | | | | |
| Improvement over usual care | +7.5% | +10% | +15% | +25% | +50% |
| ICC=0.05 | 0.72 | 0.89 | 0.99 | >0.99 | >0.99 |
| ICC=0.10 | 0.65 | 0.84 | 0.98 | >0.99 | >0.99 |
| ICC=0.15 | 0.59 | 0.79 | 0.97 | >0.99 | >0.99 |

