11.1 Primary Efficacy Analysis

The primary efficacy analysis is restricted to CAPTURE+ participants, denoted in section 9.3 as population 1 (Primary Analysis Population). The primary analysis will be to compare the average cluster sample proportion (average proportion of CAPTURE+ patients per practice meeting composite endpoint) between intervention arms. Practices that do not identify any CAPTURE+ subjects will not contribute to this analysis. A two-sample test comparing average cluster sample proportions will be used that explicitly takes into account correlation between individuals treated within the same practice. A two-sided p-value < 0.05 will be considered statistically significant. This analysis corresponds to a generalized estimating equation (GEE)⁴ regression analysis with (1) individual-level binary composite outcome data, (2) CAPTURE intervention group as a covariate, (3) practice id used to identify correlated outcomes, (4) exchangeable correlation matrix that assumes similar correlation between all composite outcome results for patients within the same practice, and (5) an identity link function so that the coefficient parameter corresponding to CAPTURE intervention group represents a difference in outcome probability. The primary analysis would then correspond to a test for whether the CAPTURE intervention group parameter is non-zero.

Technical Details of the Primary Analysis:

This analysis is restricted to CAPTURE+ participants (Primary Analysis Population)

Let $\pi_{ij} = P(\text{Participant } j \text{ from Practice } i \text{ Meets the Primary Endpoint})$.

Let $CAPTURE_i = I(\text{Practice } i \text{ Received Basic COPD plus CAPTURE education intervention})$

Let PRACTICE take on values $i = 1, \dots, 100$ denoting the enrolled practices

For the primary analysis, the GEE model takes the form

$\pi_{ij} = \beta_0 + \beta_1 CAPTURE_i$, where binary outcomes from the same practice are assumed to follow a compound symmetry correlation structure.

R code for the Primary Analysis:

If the R dataset representing CAPTURE+ patients is called **final** and variables are

MetComp=1 if individual met primary (composite) outcome, 0 otherwise

CAPTURE=1 if individual was from a practice randomized to the Basic COPD plus CAPTURE education intervention, 0 otherwise

Practice is a variable with values $1, \dots, 100$ denoting the enrolled practices

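### The GEE has no small-sample variance correction, so confidence intervals in practice-level subgroups with about 10 or fewer practices per arm can be too narrow

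*SAP*

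**What the plan says.** SAP 9.4 tabulates the intervention effect with a 95% interval and p-value in each predefined subgroup, displays the results in forest plots, and says the method follows SAP 11.1. "Practice level covariates include practice type" (five categories), rural location, residency status, in-house spirometry and number of clinicians (three categories). The set is repeated for participants with baseline on or before March 19, 2019 and for those after it. SAP 11.2 repeats the analyses in populations 2-8.

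SAP 11.1 gives a geeglm call with identity link and exchangeable correlation, and no variance option. Its criterion is "A two-sided p-value < 0.05 will be considered statistically significant". SAP 11.2 names "GEE robust sandwich estimation of variability within clusters" for model selection in the multivariable models; Protocol 9.3.2 says the same of its GEE secondary analyses. A t distribution for an effect estimate appears only where multiply imputed results are pooled (end of SAP 11.2). Neither document sets a minimum number of practices for a subgroup analysis.

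**The concern.** The sandwich variance is built from squared practice-level residuals around a fitted mean. With few practices those residuals are too small, and a normal reference ignores the uncertainty in the variance itself. Both effects make intervals too short. With about 50 practices per arm this is minor. With 10 or fewer it can matter, and the plan's own subgroup scheme leads to counts of that order.

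At stake are the intervals in the forest plots, the subgroup p-values, and the p < 0.05 selection rule for practice-level covariates, which are estimated from between-practice information. A reader would take a stated 95% interval at face value when it may behave like an 85-90% one.

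**Working it through.** **1. The plan's own figure.** SAP section 8 sets the design: "These calculations assume a type I error of 5% and that the control arm meets the composite endpoint in 5% of CAPTURE+ patients". It considers "intra-cluster correlation coefficient (ICC) values of 0.05, 0.10 and 0.15", with 5 CAPTURE+ patients per practice, and says "Therefore, our power calculations are based on 44 clusters per intervention arm".

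- Effective n per arm = 44 × 5 / (1 + (5 − 1) × ICC). At ICC 0.10: 220 / 1.4 = 157.1.
- For 5% versus 15%: null SE = √(2 × 0.10 × 0.90 / 157.1) = 0.0338; alternative SE = √((0.0475 + 0.1275) / 157.1) = 0.0334.
- Power = Φ((0.10 − 1.96 × 0.0338) / 0.0334) = Φ(1.01) = 0.84, as the SAP states.

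The nine cells for +7.5, +10 and +15 points all reproduce within 0.02. The design inputs are therefore understood, and the full-trial calculation is not in question.

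**2. How few practices.** Counts per subgroup are not in the documents, but bounds follow.

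- Five practice types over 100 practices: 100 / 5 = 20, so the smallest level has at most 20 practices and its smaller arm at most 10 (assuming all five levels are occupied).
- Randomization is stratified by PBRN only (SAP 7.3), so arms within a type may be unequal.
- Earlier cohort: SAP Table 6 lists 15 + 15 + 9 + 6 + 11 + 12 = 68 practices a full year after the cut-off. Table 8 shows that PBRN F (12 practices) had no eligible patients until September 2020, so it contributes none. At most 56 practices remain. 56 / 5 = 11.2, so the smallest type has at most 11, and at most 5 in its smaller arm.
- Populations 2-8: SAP 13.1 reports roughly 2 spirometric COPD patients per practice, and Protocol 9.3.2 drops practices with none.

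**3. Closed-form benchmark.** With k equal-sized practices per arm and roughly normal practice proportions, the uncorrected variance averages (k − 1)/k of its target. Coverage is then P(|t| < 1.96 × √((k − 1)/k)) on 2k − 2 degrees of freedom.

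- k = 5: limit 1.753, 8 df, 88.2%
- k = 10: limit 1.859, 18 df, 92.1%
- k = 25: limit 1.920, 48 df, 93.9%
- k = 44: limit 1.938, 86 df, 94.4%

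**4. Simulation.** Unequal practice sizes make this worse. Beta-binomial outcomes, variable cluster size (mean 10), ICC 0.10, identity-link exchangeable GEE, 2,500-4,000 replicates per cell. Practices per arm are assumed. Cells show coverage with the uncorrected sandwich and z, then with Mancl-DeRouen and t.

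| Practices per arm | 30% vs 40% | 5% vs 15% |
|---|---|---|
| 3 | 75.7% → 96.7% | not reported |
| 5 | 84.7% → 95.8% | 85.0% → 96.1% |
| 10 | 90.7% → 95.6% | 90.3% → 95.3% |
| 20 | 94.0% → 96.0% | 93.0% → 95.1% |
| 44 | 94.1% → 95.1% | not reported |

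Unequal arms at 30% versus 40%, uncorrected: 4 vs 6 practices 84.7%; 3 vs 7, 80.2%; 2 vs 8, 74.0%; 6 vs 14, 90.3%. Over all settings with an effect or with rates of about 10% or more, the range is about 90-93% at 10 per arm and 83-90% at 5 per arm.

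**5. The exception.** At 5% in both arms, among data sets with an event in each arm, uncorrected coverage was 94.3-97.3% at 5-10 practices per arm, so not clearly low. There the fit was degenerate in 8-60% of replicates. A separate run (mean 6.5 per practice) had an arm with no events in 40%, 17% and 5% of trials at 6, 10 and 15 practices per arm.

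**The case against.** The strongest reply has four parts.

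- **The sandwich sentence is about model selection.** This stands. The subgroup intervals rest on SAP 9.4 and the 11.1 code, and that geeglm returns an uncorrected sandwich by default was inferred, not confirmed by running R. No other GEE variance is named in either document.
- **Subgroup counts are not given.** This stands too. A reader might infer that every practice-level subgroup is affected; the documents do not support that. Two-level factors with about 25 practices per arm lose only 1-2 points.
- **The intervals are not always too narrow.** A reader might infer that they are. At the SAP's planning rate of 5%, if it held in both arms, they are not; the difficulty there is arms without events. Mancl-DeRouen with t is then over-conservative (type I error 0.3% at 6 and 0.9% at 10 practices per arm).
- **The analyses are exploratory and already hedged.** SAP 9.7 says such p-values will be read with caution, and Protocol 9.1.2.2 calls the secondary practice-behavior analyses exploratory. This limits the consequence. But that caution follows from the absence of multiplicity adjustment, and the same section relies on confidence intervals to summarize treatment differences. It does not tell a reader that an interval under-covers.

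**Conclusion.** The point holds for the smallest practice-type levels and for the further splits by cohort and population. Followed as written, and if geeglm's default is the uncorrected sandwich, the plan would report nominal 95% intervals there that cover about 90-93% with 10 practices per arm and 83-90% with 5. This assumes event rates of about 10% or more, or a true effect such as 5% versus 15%. At 5% in both arms, non-estimability is the main problem.

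It would be wrong to read this as a flaw in the primary analysis: at 44 practices per arm coverage is about 93-94%. No planned primary conclusion depends on the correction, so this is a desirable improvement rather than an essential one.

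**What to change.** Add to SAP 9.4 and 11.2 that GEE subgroup, cohort and secondary-population analyses, and multivariable model selection, use a bias-corrected sandwich (Kauermann-Carroll or Mancl-DeRouen, one chosen in advance) with a t reference on practices minus parameters. State that when an arm has no events, only descriptive proportions are reported. Leave the primary test in SAP 11.1 as it is.

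The cost is a few sentences and a software option; no new data are needed. Intervals become clearly wider where practices are few: about 35% (Kauermann-Carroll) to 57% (Mancl-DeRouen) at 5 per arm, 14% to 21% at 10, and 6% to 9% at 20. Some conservatism at low event rates must be accepted.
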